2.5.3. Dropouts, Non-Compliant Patients and Follow-up

- **Dropout from study:** Patients will be considered to have dropped out from the study only if they **declare they are no longer interested in further participation and not willing to return for any study visits, or are deceased**. If patients are not willing to return for any study visits, no further information will be collected on those patients. We anticipate that a few patients may drop out due to unwillingness to continue or death. In case of patient dropout, the patient dropout form should be filled out.

[figure not shown]
If death is considered to be related to the study drug, the patient will be counted as a treatment failure. If death is not related to the study drug, the patient will be counted as a dropout. This would be at the discretion of the Medical Monitor.

- **Non-compliant Patients:** Patients who stop the study treatment for reasons other than efficacy, tolerability and/or safety (i.e. fear of potential side effects) but are willing to return for study visits, are not considered dropouts. Also, if patients miss study visits, and do not respond to contact, they are not considered dropouts. These patients will be considered **non-compliant patients**, and will be encouraged to return for subsequent study visits regardless of whether or not they are taking study medication, especially the 6 month visit (Phase I and Phase II).

It should be noted that missing a visit does not mean that a patient has dropped out of the study. These patients are considered to be non-compliant. For example, if they missed the 1 month visit, every attempt will be made to bring them back as soon as possible and to continue with subsequent visits. Also, a non-serious adverse event or discontinuation of study medication does not mean that the patient has dropped out and they should continue to be followed according to the protocol, as they may be able to resume treatment. Even if the patient is not willing to resume treatment, but is willing to return for study visits they are not considered dropouts.

- **Following Patients who fail prior to Phase I & Phase II (6 months):** If patients are declared a treatment failure prior to Phase I or Phase II 6 Months, every effort should be made to bring the patient back for the 6 month visit. Note, that patients who are declared treatment failure, and are switching from Phase I to Phase II will already be followed.

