For all patients, oral prednisone will be tapered gradually according to Standardization of Uveitis Nomenclature (SUN) guidelines (see Table 6). As it takes 6-8 weeks for the study medications to take full effect, it is expected that inflammation may become uncontrolled with a corticosteroid taper in some patients during the first 3 months of the study. This does not necessarily mean that the randomized treatment has failed, since more time may be needed to ensure the drug has reached its full effect. If the study ophthalmologist believes that continued treatment is futile prior to the primary endpoint, treatment failure may be declared and the patient should enter Phase II. If this occurs in Phase II, treatment failure will be declared and the patient should be treated according to best medical judgment. However, all patients should be followed up to their 6th month assessment in Phase II.

At any point in Phase I or Phase II, investigators have the option of reducing the prednisone dose, and following a faster taper, if the patient is experiencing severe side effects. However, it is strongly encouraged that investigators follow the corticosteroid tapering guidelines. If **absolutely medically necessary**, the investigator may digress from the protocol and reduce steroids below 7.5 mg/day in the first six months, but this is strongly discouraged.

The corticosteroid tapering schedule for Phase I (6-12 months) is optional, and physicians may taper patients as they deem medically acceptable. It is not mandatory for patients to reduce down to 0mg of prednisone by 12 months. In general, a rapid taper in Phase I months 6-12 is not recommended due to issues of adrenal insufficiency.

Table 6: Tapering schedule for oral prednisone: Phase I or if starting new medication in Phase II*

Dose (mg/day)	Duration (weeks)	Decrement (mg/day)
60	2 – 4 ¹	10
50	1	10
40	1	5
35	1	5
30	1	5
25	1	5
20	1	2.5
17.5	1	2.5
15	1	2.5
12.5	1	2.5
10	1	2.5
7.5	hold*	

NOTE: Begin patients at 1mg/kg or 60 mg/day, whichever is less. For Phase I hold patients at 7.5 mg/day, up to the end of 6 months.

*If starting Phase II and failed Phase I due to efficacy.

If uveitis does not improve at the end of the first 4 weeks, use best medical judgment regarding supplemental treatment (e.g. pulse dose treatment, corticosteroid injections, additional immunosuppressives).

Table 7: Optional tapering schedule Phase I (6-12 months)

Dose (mg/day)	Duration (weeks)	Decrement (mg/day)
7.5	1*	2.5

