4.1.2. Phase II: Rescue treatment

In case of the first randomized treatment failure due to intolerability or lack of efficacy within the first six months of treatment, the treatment assignment will be switched to the alternate treatment. At this point, the patient will receive the antimetabolite not originally randomized to and will be followed an additional 6 months or until failure of the second treatment.

Patients will be given 2 weeks to enter into Phase II after treatment failure in Phase I. If patients do not enter within the 2-week window, they should be treated according to best medical judgment of their physician. If the physician believes a patient would benefit from treatment in Phase II, but there is an exceptional circumstance preventing the patient from entering Phase II within the 2-week window, contact the Coordinating Center for assistance.

Guidelines for Visit Schedule II

- Day 1 corresponds to the Baseline-II visit, which is also the first day the patient receives rescue treatment with the medication not initially received. Day 1 may be its own visit date (i.e. if within 2 weeks of the end of Phase I). Alternatively Day 1 may be the same day as the last day of Phase I. All study forms should indicate what visit it is for Phase I and what visit it is for Phase II, if applicable. See the following example below.

Phase	 1	 2								
Visit	 Baseline	 Two weeks	 Non-study visit (treatment failure only)							
Month:	 1	 2	 3	 4	 5	 6	 9	 12		

- Visit dates are determined based on the date of the Baseline-II visit (which may be the same date as Phase I treatment failure), and may not be changed.
- The Baseline-II visit form should be completed to gather information on any changes in health status or medications.
- There should be a minimum of 2 weeks between each study visit.
- Data for the follow-up visits may be collected anytime within the visit window.

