4.1.3. Non-study visits

Despite the regular follow-up outlined in the visit schedules above, it is anticipated that some patients will have inflammation that is difficult to control or be intolerant to the drug, leading to additional visits. These additional visits may not fall within the study visit window. It is possible that the circumstances leading to such visits may result in changes to oral or topical corticosteroid dose, or a declaration of treatment failure and a need for rescue treatment. If treatment failure is declared at a non-study visit, all of the forms required at the time treatment failure is declared should be completed.

Guidelines for non-study visits

- Any changes to oral or topical corticosteroid dose will be noted on the appropriate form during the next scheduled study visit.
- If a treatment failure is declared at a non-study visit during follow-up while being treated during...
 - Phase I (initial randomized treatment): Record a treatment failure using Treatment Assessment Form. Perform Baseline II visit at this time or within 14 days. Phase II rescue treatment can start immediately.
 - Phase II: Record a treatment failure using the Treatment Assessment Form. Patient should continue to be followed until 6 months and 6th month data collected.
 - If treatment failure is declared at a non-study visit, an attempt should be made to collect as much information as possible, including the forms listed in Section 4.2.

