2.3 Specific Aims

2.3.1 Specific Aim 1

Primary Objective. The primary objective of the study is **to establish which immunosuppressive treatment, methotrexate or mycophenolate mofetil, results in a higher rate of corticosteroid-sparing treatment success, on an intent to treat basis.** Specifically, we will compare the fraction of subjects who achieve treatment success at six months (as defined in the Manual of Operations Section 2.5.1) between the two groups.

Primary Outcome. The primary outcome for Specific Aim 1 will be the difference in the proportion of patients assigned to mycophenolate mofetil vs. methotrexate who achieve treatment success (as defined in the Manual of Operations Section 2.5.1).

Patients who experience success at 6 months with the drug to which they were originally randomized (in Specific Aim 1) will continue on the same drug for an additional 6 months. This will be called Phase I (6-12 months). Patients will then be seen every 3 months (and will be examined at 9 months and at 12 months), until success at 12 months or treatment failure at any time. Patients who fail treatment before 12 months with the initial drug will be removed from the study and treated according to best medical judgment.

Secondary Objectives

- To determine whether patients exhibit a difference in time to control of inflammation within the first six months.
- To determine whether patients exhibit a difference in time to corticosteroid sparing control of inflammation within the first six months.
- To evaluate the proportion of patients achieving treatment success at 5 months and sustaining, for at least 28 days, to 6 months.
- To evaluate a difference in control of inflammation in the posterior/pan anatomic locations only, assessed at by six months.
- To evaluate a difference in control of inflammation in the interior and anterior/intermediate anatomic locations only, assessed at by six months.
- To determine whether there is a change in best spectacle-corrected visual acuity at six months.
- To determine whether patients treated exhibit a difference in health related quality of life at six months.
- To determine if there are differences in discontinuing treatment due to each of the following reasons: safety, intolerability or lack of efficacy at six months.
- To determine whether patients exhibit a difference in the proportion of patients having macular edema at 6 months
- To determine whether patients exhibit a difference in macular thickness at 6 months

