Patients who experience treatment failure (as defined in the Manual of Operations) with the drug to which they were originally randomized in Specific Aim 1 will discontinue the current treatment and be administered rescue therapy with the second drug (in a masked fashion). This will be called Phase II. Treatment failure with the first drug is defined as the inability to continue taking the drug to which the patient has been randomized, either due to intolerability, safety concerns, or lack of efficacy.

Upon declaration of treatment failure, the patient will be automatically screened for Aim 2. If eligibility criteria are met, the second treatment will be administered and data will be collected for the Phase II baseline visit. Patients will then be seen every 4 weeks until 6 months or until treatment failure with the second drug. Treatment failure and success will be defined as in Aim 1. Patients who fail treatment before 6 months with the second drug will be removed from the study and treated according to best medical judgement.

Primary Outcome. The primary outcome is the fraction achieving treatment success at 6 months after starting Phase II. Treatment success is defined as in Aim 1 and described in the Manual of Operations Section 2.5.1.

Secondary Objectives. All of the secondary 6 month objectives listed for Aim 1 will be examined for Aim 2.

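### The SAP ends follow-up at early failure of the second drug while most of the protocol continues it to month 6; Aim 2 outcomes fixed at month 6 would lose those patients

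*Combined protocol and SAP*

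**What the plan says.** **Texts that end follow-up at failure of the second drug**

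- SAP 2.3.2: "Patients will then be seen every 4 weeks until 6 months or until treatment failure with the second drug", and then "Patients who fail treatment before 6 months with the second drug will be removed from the study".
- Protocol 4.1.2 (Phase II: Rescue treatment): the patient "will be followed an additional 6 months or until failure of the second treatment". Protocol Section 1 (Introduction to trial) says the same in substance.

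**Texts that continue to month 6**

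- Protocol 2.5.3, on failure before month 6 in either phase: "every effort should be made to bring the patient back for the 6 month visit".
- Protocol 3.2.1, on futility in Phase II: "all patients should be followed up to their 6th month assessment in Phase II". The rescue-taper directions in the same section repeat the request.
- Protocol 4.1.3, on Phase II failure at a non-study visit: "Patient should continue to be followed until 6 months and 6th month data collected".
- Protocol 2.5.2 (safety failures) asks for month-6 data and imaging in both phases, and 3.1.2 (tolerability failures) asks for follow-up to the month-6 assessment in both phases.
- Protocol 5.1 wants quality-of-life questionnaires at failure and again at month 6, in both phases.

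**What Aim 2 analyses**

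SAP 2.3.2 carries the Aim 1 list across: "All of the secondary 6 month objectives listed for Aim 1 will be examined for Aim 2". That list includes macular edema, macular thickness, vitreous haze, acuity, quality of life and adverse events.

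**The concern.** The two sets of instructions cannot both be followed. A site or programmer working from SAP 2.3.2 would have no month-6 visit for a patient who failed the second drug early. Turning to the protocol does not settle the matter, because the protocol contradicts itself.

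The patients concerned are chosen by their outcome after Phase II began. Where an analysis needs a month-6 measurement and has no stated alternative, leaving them out compares the two rescue groups among patients who had not failed early. The group that fails more often would lose more patients. Adverse events between failure and month 6 would also go unrecorded for them.

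**Working it through.** **1. The plan's own numbers.** SAP 3.4.2 uses n = N0 × r1 × (1 − s) × r2, with N0 = 108, r1 = 0.9, r2 = 0.95 and first-line success s of 40% and 60%.

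- First-line success 40% (then mycophenolate rescue): 108 × 0.9 × 0.60 = 58.3 enter; × 0.95 = 55.4 complete.
- First-line success 60% (then methotrexate rescue): 108 × 0.9 × 0.40 = 38.9 enter; × 0.95 = 36.9 complete.

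These match the SAP table. The SAP's power formula with 58 and 38 patients and success of 0.42 and 0.15 gives Φ(0.27 / √(0.15 × 0.85/38 + 0.42 × 0.58/58) − 1.96) = 0.874, against 0.87 stated. The only deduction within Phase II is 5% loss to follow-up, so the planning keeps early failures in the denominator.

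**2. Which Aim 2 outcomes depend on a month-6 visit**

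| Outcome | Value for an early failure | Source |
|---|---|---|
| Treatment success (primary) | Known non-success | Protocol 2.5.1 requires no failure at any point; SAP 2.3.2 uses the Aim 1 definition |
| Acuity | Taken at failure or month 6 | SAP 3.2.1; 3.2.2 item 4 |
| Quality of life | Taken at failure or month 6 | SAP 3.2.2 item 5 |
| Vitreous haze | Partly covered: eye exam required at failure, and one alternative analysis uses the final observation; the objectives are set at 6 months | Protocol 4.2, 4.6.1; SAP 2.3.1; 3.2.2 item 12 |
| Macular edema, macular thickness | None stated; set at 6 months | SAP 3.2.2 items 8 and 9 |
| Adverse events | Recorded up to failure; later events not | Protocol 4.2; SAP 2.3.1, 7.2.1 |

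A failure-visit OCT cannot be relied on to fill the gap. Protocol 4.2 marks the OCT form at failure as applicable-only, and the minimum form set for failure at a non-study visit (4.6.3) leaves it out.

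**3. Size.** Let p be Phase II success and f the share of failures that occur before month 6. The proportion without a month-6 value is f × (1 − p). SAP 3.4.2 gives p = 0.42 and 0.15, so about 55.4 × 0.58 = 32 and 36.9 × 0.85 = 31 patients fail. The documents do not give f, so a range is shown.

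| Assumed f | Mycophenolate rescue (of 55.4) | Methotrexate rescue (of 36.9) |
|---|---|---|
| 25% | 14.5% (8.0) | 21.3% (7.8) |
| 50% | 29.0% (16.1) | 42.5% (15.7) |
| 75% | 43.5% (24.1) | 63.8% (23.5) |

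If f is equal in the two groups, the ratio of the proportions is 0.85/0.58 = 1.47.

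A lower anchor comes from the first-line discontinuation rates in SAP 3.4.2: mycophenolate 4% + 5% = 9% and methotrexate 13% + 5% = 18%. Applied to Phase II, with no futility failures, these give about 5.0 of 55.4 and 6.6 of 36.9.

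**The case against.** The best case for leaving this alone has four parts.

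- **Most outcomes are safe.** A reader might infer that Aim 2 as a whole becomes a comparison of non-failures. The documents do not support that. The primary outcome, acuity and quality of life all have a defined value for an early failure, and haze is partly covered. SAP 3.3.3 also repeats final-outcome analyses with all available data. This part stands, and it confines the point to macular edema, macular thickness, part of haze, and adverse events after failure.
- **Safety data are not erased.** The adverse-event checklist is required at Phase II failure, and the safety population (SAP 4.1) is everyone who took any study drug. This also stands. What is lost is the period from failure to month 6, not events already recorded.
- **The protocol governs conduct.** The SAP defers to it for definitions, and Protocol 4.4.3 wants forms completed whether or not the patient is taking medication. No SAP rule excludes visits made after failure. This carries weight, but Protocol Section 1 and 4.1.2 stop at failure as the SAP does, so deferring to the protocol gives no single answer.
- **The size is uncertain.** Protocol 2.5.2 judges efficacy at 6 months and reserves futility for hopeless cases, so early failures may be few. This is fair, and it is why the lower anchor of 9% and 18% is given beside the range.

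A reader might also see the same contradiction in SAP 2.3.1, which says of months 6 to 12: "Patients who fail treatment before 12 months with the initial drug will be removed from the study". The protocol texts set out here concern the month-6 visit, and Protocol 5.1 accepts an earlier failure assessment in place of the 12-month questionnaires. Keeping those patients to month 12 would be a design preference that adds a visit, so it is not part of this point.

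**Conclusion.** The SAP and most of the protocol contradict each other on follow-up after early failure of the second drug, and the protocol also contradicts itself. If the SAP sentence is followed, Aim 2 macular edema and macular thickness would be compared in a sample selected on a post-baseline outcome. Month-6 haze would share the problem in part, and adverse-event follow-up would be shorter for the patients who failed.

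The gap could be anywhere from about 9% and 18% of the mycophenolate-rescue and methotrexate-rescue groups (first-line intolerance and safety rates only) to 43.5% and 64% (three quarters of failures early). These figures assume the SAP's 42% and 15% success. The table also assumes the same early share in both groups.

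The Aim 2 primary comparison is sound as defined, but the scoring rule should be explicit. SAP 3.2.2 expressly codes as 0 only discontinuations for intolerance or adverse events, and SAP 3.5 describes complete cases as those with six-month follow-up. A programmer could therefore mistake a removed futility failure for a missing value, although Protocol 2.5.1 makes it a failure and SAP 3.5 limits itself to loss to follow-up and dropout. Severity: minor to moderate.

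**What to change.** 1. Reconcile SAP 2.3.2, Protocol Section 1 and Protocol 4.1.2 with Protocol 2.5.2, 2.5.3, 3.1.2, 3.2.1 and 4.1.3, so that early Phase II failures remain in study follow-up and data collection to the Phase II month-6 visit. Treatment decisions after failure stay as the protocol has them.
2. State in SAP 3.2.3 that a Phase II failure before month 6, for any reason including futility, is scored 0 in the Aim 2 primary analysis.
3. State that the month-6 values of these patients are used in the Aim 2 secondary analyses set at month 6, and that their adverse events to month 6 enter the safety analyses.

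The cost is wording in the two documents. Most of the protocol already requires the visits, so there is almost no added burden on sites or patients.

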2.4 Randomization

2.4.1 Stratification between sites

Patients will be recruited from nine sites: [REDACTED]

[REDACTED] (see Manual of Operations Section 2.2 for details). Patients will be randomized to two treatments (arms): methotrexate (X) or mycophenolate mofetil (Y). The treatment protocols are specified in the FAST Uveitis Trial Manual of Operations.

Within each site, assignments will be conducted using a block randomization scheme with randomly varying block sizes.

2.4.2 Randomization list

Lists of sequential randomization assignments will be prepared for each site. The randomization lists consist of a unique identifier for each patient, together with the assignments to treatment arms. The assignment of patient ID numbers and randomization is thus performed on enrollment.

The randomization lists for sites will be prepared by the [REDACTED] site (see Section 10.3) and sent to the Emergency contact at each site to be used only in case emergency unmasking is needed for patient safety.

They will also be sent to hospital/clinic staff who are responsible for telling the study coordinators the treatment assignment for each patient after the patient is enrolled and the study ID has been assigned. At these sites she will verify patient treatment assignment as a quality assessment.

A backup copy of the full randomization list for all four sites will be maintained by [REDACTED] [REDACTED] This list will be maintained as a hard copy stored in a locked file cabinet at the [REDACTED] site, and to be used only in case emergency unmasking is needed for patient safety.

Distribution of the randomization list to [REDACTED] will be accomplished using the [REDACTED] encrypted email provision. Email is encrypted using the Advanced Encryption Standard (NIST FIPS 197) whenever the first four characters of the subject line are PHI: The sender is notified when the recipient receives a secure email; the recipient receives a notification of a secure email and can view it using the [REDACTED] Secure Messenger website. We have successfully used this method in previous clinical trials [REDACTED] [REDACTED]. The randomization lists will each contain more randomization assignments than needed. Successively recruited patients will receive sequential

assignments from the list. The long list provides a measure of added safety in case one of these sites recruits far more patients than expected relative to the other site.

As discussed below, the randomization lists will be provided as Excel® worksheets. No technical knowledge will be required to use these lists.

Update: starting 18 January 2017, all patients will be randomized using the REDCap database. Coordinators can access only the randomization lists for their site. When patients are enrolled, the ID is logged in REDCap and the system provides the medication assignment. All emergency contacts have access to the REDCap database for their site in case of an emergency when unmasking is needed for patient safety. The REDCap database contains assignments for all previously enrolled patients. All previous randomization lists were deemed void and were destroyed. Each site submitted a certification of destruction form.

